3.4. Randomization and Blinding

Randomization will be used to avoid bias in the treatment assignment, to increase the likelihood that known and unknown attributes (e.g., demographics and baseline characteristics) are evenly balanced across treatment groups, and to enhance the validity of statistical comparisons.

Participants who meet eligibility criteria will be randomly assigned at Baseline (Visit 2) to receive pridopidine or placebo in a 1:1 randomization using an Interactive Response Technology (IRT), based upon the stratification variables of HD stage (HD1 or HD2) and use of neuroleptics (Yes/No).

This is a double-blind study where all participants, site staff, Sponsor, Clinical Research Organizations (CROs) and vendors involved in the conduct, data management or analysis of the study will remain blinded to treatment assignments. At the End of the Main Study when the last participant has completed the Week 65 visit or has withdrawn from the study, following database lock, the treatment assignment will be unblinded for analysis.

The exceptions to above blinding are the unblinded statistician and programmer who will generate the analyses for the SMC and will not otherwise be involved in the trial, the vendor personnel responsible for configuration of the IRT system, and the drug packaging and labeling team (unblinded personnel) who will distribute the pridopidine or placebo drug. Each of these groups will have standard operating procedures (SOPs) or study specific plans in place for maintaining the treatment blind. Drug concentration information that would unblind the study will not be reported to investigative sites or blinded personnel until the study has been unblinded.

The IRT system will be programmed with blind-breaking instructions. In case of an emergency, the Investigator has the responsibility, after consultation with the medical monitor, for

determining if unblinding of a participant's study drug assignment is warranted. Participant safety must always be the first consideration in making such a determination. If a participant's study drug assignment is unblinded, the Sponsor must be notified within 24 hours after breaking the blind. The date and reason that the blind was broken must be recorded in the source documentation and CRF, as applicable. The responsible CRO will also be notified immediately of such unblinding without revealing details of the participant's treatment.

Appropriate personnel at the Sponsor or sponsor designee will unblind suspected unexpected serious adverse reactions (SUSARs) for the purpose of regulatory reporting. The Sponsor will submit SUSARs to Regulatory Agencies in a blinded or unblinded fashion according to local regulations. The Sponsor will submit SUSARs to Investigators in a blinded fashion. Details of how the blind is maintained during PK analysis will also be included in the blinding/unblinding plan.

3.5. Sequence of Planned Analyses

3.5.1. Interim Analyses

No interim analysis is planned for this study. The analyses after the last participant completes Week 65 will be considered the final analyses of the Main Study. See Section [3.5.3](#) below.

3.5.2. Analyses for Safety Monitoring Committee Meetings

During the conduct of the Main Study, an independent SMC will be monitoring the safety, tolerability and/or efficacy (if needed).

Details of what data will be reviewed and when during the study will be included in the SMC Charter.

3.5.3. Analyses and Reporting of Main Study Results

All final, planned Main Study analyses specified in this SAP will be performed only after database lock for the Main Study after the last participant has completed the Main Study. The randomization codes will not be unblinded until this SAP has been finalized and the database locked.

The Main Study is considered to be complete when all participants who have signed informed consent, been randomized, and treated have completed at least Week 65 of the study or discontinued from the study earlier.

The regulatory submission will be based on the analyses of Main Study data. OLE analyses as planned in Section [3.5.4](#) will be provided as update materials after submission.

3.5.4. OLE Analyses

OLE analyses on the data collected during the OLE period will NOT be performed at the database lock for the Main Study. The final analyses for the OLE will be performed after the last participant has completed the EoS Visit and the database has been locked for the OLE period. The analyses will be used to assess the durability of treatment effect, safety and tolerability of pridopidine during the OLE period.

Interim analyses may be performed on OLE data prior to completion of the OLE.

Analyses using external controls such as data collected in ENROLL-HD, a longitudinal, multinational, observational registry study may be performed to contextualize the long-term effect of pridopidine on treating HD in OLE period. These analyses, if required, will be detailed in a separate SAP.

3.5.5. Other Analyses

Additional analyses may be added to this SAP which will be included in an Amendment, Appendix or Addendum.

Any exploratory analyses completed to support study analyses, which were not identified in this SAP or an Amendment, Appendix or Addendum prior to locking the database and unblinding the study, will be documented and reported in changes to the planned analyses section in the CSR.

3.6. COVID-19 Mitigation

The PROOF-HD study is being conducted during the COVID-19 pandemic and incorporates several mitigation strategies that are included in the protocol and study plans. For details, refer to the protocol Section 10.10. A brief summary is included below:

- Four (4) pre-planned virtual visits (VVs) have been incorporated into the protocol at different timepoints (performed via telephone)
- Every in-clinic visit, except Screening, Baseline, and Week 65 visits, can be converted to a VV if required (performed via telephone, smart phone, tablet or computer and home assessments by healthcare professional)
- Raters will be trained and ready to implement pre-identified remote efficacy and safety measures via telephone (see [Table 3](#)) during the pre-planned VV and during the converted VV
- Home visit by healthcare professionals will perform essential safety assessments (safety labs, urinalysis, pregnancy test, vital signs, and drug accountability) if clinic visits are converted to VVs

3.6.1. Types of Visits

- **In-Clinic Visits** – Screening, Baseline, W4, W26, W39, W52, W65, W78 (EoS/ET)
- **Pre-Planned VVs** – at Baseline, W13, W32, and W58
These have been included as a contingency plan for the integrity of the study primary endpoint and several secondary endpoints
- **Converted VVs** – In-Clinic Visits that can be replaced by VV if necessary – W4, W26, W39, and W78

Table 3: Visit Activities According to the Visit Types

Study Period Procedures and Assessments	In- Clinic Visit	Preplanned Virtual Visits (Phone)	Converted VV (Home/Phone)
Informed consent	✓	X	X

Study Period Procedures and Assessments	In- Clinic Visit	Preplanned Virtual Visits (Phone)	Converted VV (Home/Phone)
Demography	✓	X	X
Medical and psychiatric history	✓	X	X
Prior medication and treatment history	✓	X	X
Inclusion and exclusion criteria		X	X
Clinical laboratory tests (serum chemistry, hematology, and urinalysis)*	✓	X	✓ (Home Nursing Service)
Pregnancy test (for WOCBP)*	✓	X	✓ (Home Nursing Service)
Full physical and neurological examination	✓	X	X
Brief physical examination	✓	X	X
12 lead ECG	✓	X	X
Vital signs*	✓	X	✓ (Home Nursing Service)
C-SSRS (baseline version)	✓	X	X
C-SSRS (since last visit version)	✓	✓	✓ (Phone)
UHDRS-TFC*	✓	✓	✓ (Phone)
UHDRS-TMS	✓	X	X
UHDRS-IS	✓	X	X
SDMT	✓	X	X
SWR	✓	X	X
Q-Motor	✓	X	X
PBA-s (Short Form)	✓	✓	✓ (Phone)
CGI-S (modified)	✓	X	X
CGI-C	✓	X	✓ (Phone)
HDQoL-P	✓	X	✓
Benzodiazepines and antidepressants inquiry	✓	✓	✓ (Phone)
Alcohol/illicit drug use inquiry	✓	✓	✓ (Phone)
Review of tolerability to study drug prior to dose escalation	✓	X	X
Randomization	✓	X	X
Dispense/collect study drug*	✓	X	✓ (Qualified provider)
Review study compliance and adherence*	✓	X	✓ (Home Nursing Service)
Adverse event inquiry	✓	✓	✓ (Phone)

Study Period Procedures and Assessments	In- Clinic Visit	Preplanned Virtual Visits (Phone)	Converted VV (Home/Phone)
Concomitant medication inquiry	✓	✓	✓ (Phone)
Blood samples for PK analysis	✓	X	X
Plasma sample for biomarker analysis	✓	X	X
Blood sample for genetic analysis	✓	X	X
ECG	✓	X	X

X- assessment not done

✓- Yes, assessment done

* Participants who are off study drug and continue to participate in the study and have their clinic visits converted to virtual visits (by phone) will not be required to undergo UHDRS-TFC assessment or get home nursing services during the converted virtual visits.

3.6.2. Other Mitigation Strategies Incorporated

- A customized guidance to address global health emergencies and potential impact on the clinical study is included as an appendix to the protocol Section 10.10. The guidance also covers the following:
 - Consent can be given orally/remotely by the study participant
 - Study participant and person obtaining consent can sign two separate consent forms
 - Local laboratory may be used for safety labs if necessary
 - Monitoring activities may be adjusted (central monitoring, off-site monitoring, remote source data verification)
 - Prilenia and the Huntington Study Group (HSG) will continually assess whether the limitations imposed by the COVID-19 public health emergency on protocol implementation pose new safety risk to the study participants and whether it is feasible to mitigate these risks by amending the study protocol and/or procedures

3.6.3. Mitigation Strategies for Analyses of Primary and Important Secondary Efficacy Endpoints

The impact of COVID-19 resulting in treatment discontinuation is described in Section 7.1 and elsewhere in the SAP for estimand and sensitivity analyses under the ICH E9 R(1) framework and related publications^{2,3,4} (Akacha et. al., 2020; Meyer et. al., 2020). As of the SAP Version 2.0 update in November 2022, due to the minimal impact of COVID-19 on the efficacy endpoints as detailed in below sections, no additional efficacy analyses will be performed to address COVID-19 impact.

² ICH E9 R(1) “Addendum on Estimands and Sensitivity Analysis In Clinical Trials to the Guideline on Statistical Principles For Clinical Trials.” May 2021 ICH Revision 1.

³ FDA Guidance on Statistical Considerations for Clinical Trials During the COVID-19 Public Health Emergency. Guidance for Industry, August 2021. <https://www.fda.gov/media/139145/download>.

⁴ FDA Guidance on Conduct of Clinical Trials of Medical Products during COVID-19 Public Health Emergency. Guidance for Industry, Investigators, and Institutional Review Boards, March 2020. <https://www.fda.gov/regulatory-information/search-fda-guidance-documents/fda-guidance-conduct-clinical-trials-medical-products-during-covid-19-public-health-emergency>

3.6.3.1. Evaluation of the Correlation Between In-clinic UHDRS-TFC Assessment and Phone (virtual) UHDRS-TFC Assessment

In SAP v1.0, it was stated that blinded analyses will be performed to assess reliability of the virtual UHDRS-TFC by computing the intra-class correlation coefficient (ICC) assessed at Baseline in-clinic and virtually over the telephone at VV1, and that if the ICC is shown to be ≥ 0.80 , the last available virtual UHDRS-TFC assessments may be used for participants who discontinue prior to Week 65 or do not have an assessment at Week 65.

However, based on the observed high completion rate (98.9%) of in-clinic UHDRS-TFC assessments as of October 2022, the COVID-19 impact is expected to be minimal. There also may exist some heterogeneity if combining in-clinic and virtual visits as they are conducted in general 6 to 7 weeks apart. Furthermore UHDRS-TFC virtual assessments have not been previously validated. Therefore, only the in-clinic UHDRS-TFC will be used for primary and secondary analyses. Additional exploratory efficacy analyses using virtual UHDRS-TFC will be presented.

It was also stated in SAP v1.0 that if the number of participants who either discontinue from the study or have their Week 65 assessments impacted by COVID-19 was larger than planned, a blinded sample size re-estimation analysis may be conducted. Due to low discontinuation rate and minimal impact of COVID-19 on Week 65 UHDRS-TFC assessments, the blinded sample size re-estimation will not be performed.

3.6.3.2. Impact on Secondary Endpoints

As of October 2022, the completion rate of scheduled assessments is $>97\%$ for cUHDRS and TMS. The COVID-19 impact on secondary endpoints is also minimal.

3.6.4. Impact on Protocol Safety Assessments

The impact of COVID-19 on protocol deviations (PDs), medications taken, AEs and other key safety data will be summarized descriptively in corresponding safety analysis.

4. POPULATIONS /ANALYSIS SETS

4.1. Analysis Populations for the Main Study Period

The populations below are defined using the traditional approach as per ICH E9. The exact handling of intercurrent events (ICEs) for each of these are detailed further in Section 7.1 using the estimand framework per ICH E9 R(1).

4.1.1. Intent-to-Treat (ITT) Population

The intent-to-treat (ITT) population will include all randomized participants. In this population, treatment will be assigned based on the treatment to which participants were randomized, regardless of which treatment they actually received. The ITT population is the main analysis population of primary endpoint for European Medicines Agency (EMA) submission.

4.1.2. Modified Intent-to-Treat (mITT) Population

The modified intent-to-treat (mITT) population is a subset of the ITT population and will include all participants in the ITT population who received at least 1 dose of study drug and have valid in-clinic TFC scores both at Baseline and at least 1 post-baseline timepoint. The mITT population will be analyzed according to the treatment to which the participant was randomized. The mITT population is the main analysis population for primary endpoint in non-EMA submission. For all other efficacy analyses, the mITT population is the main analysis population in both EMA and non-EMA submission.

All participants who received at least 1 dose of pridopidine and have at least 1 valid in-clinic UHDRS-TFC score during the OLE period will be included in the OLE mITT population.

4.1.3. Per Protocol Week 65 (W65PP) Population

The per protocol Week 65 (W65PP) population is a subset of the mITT population and includes all participants who have a valid UHDRS-TFC at Week 65, were on study drug with compliance >80% during the study, and did not have any important PDs (document of PDs resulting in exclusion from PP population) or other events (e.g., receipt of incorrect treatment) impacting the TFC assessment. The W65PP population will be used for sensitivity analysis of the primary and select secondary endpoints at Week 65, and will be analyzed according to the actual treatment received (See Section 4.1.5 for definition of actual treatment). The W65PP population will be finalized prior to locking the database and unblinding the study.

4.1.4. Per Protocol Week 78 (W78PP) Population

The per protocol Week 78 (W78PP) population is a subset of the mITT population and includes all participants who have a valid UHDRS-TFC at Week 78, were on study drug with compliance >80% during the study, and did not have any important PDs (document of PDs resulting in exclusion from PP population) or other events (e.g. receipt of incorrect treatment) impacting the TFC assessment. The W78PP set will be used for sensitivity analysis of secondary endpoints at Week 78, and will be analyzed according to the actual treatment received (See Section 4.1.5 for definition of actual treatment). The W78PP population will be finalized prior to locking the database and unblinding the study.

4.1.5. Safety Population (SP)

The safety population (SP) will include all randomized participants who received at least 1 dose of study drug. In this population, treatment will be assigned based upon the treatment participants actually received, regardless of the treatment to which they were randomized. The safety set will be used for safety analyses and biomarker analysis.

All participants who receive at least 1 dose of pridopidine during the OLE period will be included in the OLE safety population.

The actual treatment received in the double-blind period will be pridopidine if a participant receives pridopidine for >10% of total number of doses received; otherwise, the actual treatment will be placebo. The actual treatment received in the OLE will be pridopidine to pridopidine if a participant receives pridopidine for >10% of total number of doses received in the double-blind period; otherwise, the actual treatment will be placebo to pridopidine.

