9.3.1. Main Study

Population	Description
Intent-to-Treat (ITT) population	The ITT population will include all randomized participants. The participants will be grouped as randomized.
Modified Intent-to-Treat (mITT) population	The mITT set is a subset of the ITT population and will include all randomized participants who receive a dose of study drug and have valid TFC efficacy assessments both at the Baseline visit and at least one post-baseline in-clinic timepoint. The participants will be grouped as randomized.
Per Protocol Week 65 (W65PP) population	The per protocol Week 65 set is a subset of the mITT set and includes all participants who have a valid in-clinic UHDRS-TFC at Week 65, were on study drug with compliance > 80% during the study, and did not have any important protocol deviations impacting efficacy assessment. Per protocol variations will be defined prior to unblinding the data and participants subsequently grouped as treated. The per protocol set will be used for supplementary analysis of the primary and select secondary endpoints.
Per Protocol Week 78 (W78PP) population	The per protocol Week 78 set is a subset of the mITT set and includes all participants who have a valid in-clinic UHDRS-TFC at Week 78, were on study drug with compliance > 80% during the study, and did not have any important protocol deviations impacting efficacy assessment. Per protocol variations will be defined prior to unblinding the data and participants subsequently grouped as treated. The per protocol set will be used for supplementary analysis of the primary and select secondary endpoints.
Safety population	The safety set will include all participants receiving at least one dose of study drug. The participants will be grouped according to the treatment regimen actually received. The safety set will be used for safety analyses.
PK population	The PK population will include all randomized participants who received at least 1 dose of pridopidine and have at least 1 valid PK assessment. The

Population	Description
	participants will be grouped according to the treatment regimen actually received.

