3.2.5. Biomarker Endpoints

- Evaluate the efficacy of pridopidine 45 mg bid vs. placebo as assessed by the change from Baseline to Weeks 26, 52, 65 and 78 in plasma NfL protein
- Evaluate the relationship between Baseline NfL and changes from Baseline in select efficacy endpoints
- Evaluate the relationship between changes from Baseline to Weeks 26, 52, 65 and 78 in plasma NfL and select efficacy endpoints for pridopidine 45 mg bid vs. placebo
- Proportion of participants with stabilization or improvement in change from Baseline to Week 26, 52, 65 and 78 in plasma NfL levels

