7.1.2. Analysis Populations

The ITT population is the main analysis population of primary endpoint for EMA region. The mITT population is the main analysis population for primary endpoint in non-EMA regions.

For all other efficacy analyses, the mITT population is the main analysis population in both EMA and non-EMA regions. The ITT and PP populations will also be used as sensitivity analyses to show robustness of results for select secondary endpoints.

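### SAP 4.1.5 groups the NfL treatment comparison by drug received under a >10%-of-doses rule, although NfL change is framed as efficacy, and SAP 9.1.2 leaves open which population its NfL-adjusted TFC and cUHDRS models use

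*SAP*

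**What the plan says.** SAP 4.1.5 defines the Safety Population as randomised participants with at least one dose, and says "treatment will be assigned based upon the treatment participants actually received, regardless of the treatment to which they were randomized". Actual treatment in the Main Study, it goes on, "will be pridopidine if a participant receives pridopidine for >10% of total number of doses received; otherwise, the actual treatment will be placebo". The same section adds: "The safety set will be used for safety analyses and biomarker analysis". Protocol 9.3.1 is narrower: "The safety set will be used for safety analyses", with no mention of biomarkers.

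The first biomarker endpoint in SAP 3.2.5, which concerns plasma NfL, is worded as efficacy: "Evaluate the efficacy of pridopidine 45 mg bid vs. placebo as assessed by the change from Baseline to Weeks 26, 52, 65 and 78". SAP 7.1.2 says "For all other efficacy analyses, the mITT population is the main analysis population" in both regions and makes no exception for NfL. SAP 4.1.2 groups mITT as randomised, and 4.1.1 does the same for ITT.

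SAP 9.1.2 contains the NfL models and names no population. Objective (1) compares the arms on log2(NfL). Objective (2) models change in TFC, cUHDRS, Q-Motor, TMS, SDMT and SWR with Baseline log2(NfL) as a covariate, and reports a pridopidine-placebo difference with CI and p-value at each visit. Objective (3) relates change in NfL to change in the clinical endpoints. SAP 7.4.3 adds subgroup analyses of log2(NfL), again without saying which population applies.

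**The concern.** Drug actually received is settled after randomisation. An arm comparison built on it no longer rests fully on the allocation, and the reasons for a supply error need not be unrelated to outcome. The 10% cut-off is also lopsided. A placebo-randomised participant becomes pridopidine with slightly more than a tenth of doses active, while a pridopidine-randomised participant becomes placebo only at a tenth or less. That is a cautious rule for attributing adverse events. In an efficacy contrast it can put a mostly-placebo participant in the active group.

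The second issue is ambiguity. Someone programming Objective (2) could use the Safety Population as treated, because the models sit in the biomarker section, or mITT as randomised, because the outcome is TFC or cUHDRS. The NfL-adjusted TFC difference and the main TFC analysis could then come from differently composed arms without the tables making that obvious. The same applies to the median-Baseline-NfL subgroup of the primary endpoint (SAP 7.3.2) and the median-NfL split at the end of 9.1.2.

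**Working it through.** The plan gives no figure to reproduce on this point. The check has three parts.

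**1. The population rules side by side**

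| Analysis | Population | Grouping | Source |
|---|---|---|---|
| Primary, EMA | ITT | randomised | SAP 4.1.1, 7.1.2 |
| Primary, non-EMA; other main efficacy | mITT | randomised | SAP 4.1.2, 7.1.2 |
| Per-protocol repeats | W65PP, W78PP | received | SAP 4.1.3, 4.1.4 |
| Biomarker | Safety | received | SAP 4.1.5 |
| Objective (2) on TFC, cUHDRS etc. | not named in 9.1.2 | 4.1.5 or 7.1.2 | SAP 9.1.2 |

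SAP 7.1.1 applies a treatment-policy strategy to exploratory efficacy endpoints measured as change from Baseline. The estimand this follows (SAP 7.2) defines treatment by allocation. Grouping by drug received does not fit that definition.

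**2. How much wrong drug triggers relabelling**

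Inputs: one capsule daily for 2 weeks, then two daily (SAP 3.1); 60 capsules per bottle, inferred from SAP 8.3, where 50% of a lost bottle is 30 capsules. Full compliance is assumed.

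- Doses to Week 65: 14 + 63 × 14 = 896, so the threshold is 89.6.
- Doses to Week 78: 14 + 76 × 14 = 1078, so the threshold is 107.8.
- One wrong bottle: 60/896 = 6.7%, or 60/1078 = 5.6%. A completer is not relabelled. A participant with fewer than 60/0.10 = 600 doses in total is.
- Two wrong bottles: 120/896 = 13.4%, or 120/1078 = 11.1%. Relabelled.
- Wrong supply from Baseline to Week 4 (14 + 28 = 42 doses): 4.7% or 3.9%. Not relabelled.
- Wrong supply from Week 26 to Week 39 (13 × 14 = 182 doses): 20.3% or 16.9%. Relabelled.

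**3. Effect on the arm difference**

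The SAP version history gives 499 randomised, so take n = 250 per arm. Let k placebo-randomised participants be relabelled as pridopidine; k is an assumption, because the documents give no count.

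*Selection.* Assume no true effect, and that those k participants differ from the rest by s units on average. The arm difference moves by ks/(n + k) + ks/(n − k). With s = 1:

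- k = 1: 1/251 + 1/249 = 0.008
- k = 2: 2/252 + 2/248 = 0.016
- k = 5: 5/255 + 5/245 = 0.040
- k = 10: 10/260 + 10/240 = 0.080

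On TFC, the value at k = 5 is 0.04 points, against a design difference of 0.7 (SAP 3.3).

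*Dilution.* Let f be the share of active doses in those k participants, and assume the effect is proportional to f. The true contrast is reduced by k(1 − f)/(n + k) if grouped as received and by kf/n if grouped as randomised. With k = 5:

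- f = 0.1: 5 × 0.9/255 = 1.8% as received; 5 × 0.1/250 = 0.2% as randomised.
- f = 0.9: 5 × 0.1/255 = 0.2% as received; 5 × 0.9/250 = 1.8% as randomised.

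Whatever f is, the loss is at most k/n: 0.4% for k = 1, 0.8% for k = 2 and 2% for k = 5.

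**The case against.** The strongest defence is that 4.1.5 is a specific, prespecified rule for biomarkers. NfL has its own endpoint class (SAP 3.2.5) and its own section (SAP 9), and a specific rule can stand beside the general efficacy rule in 7.1.2. The protocol's narrower use of the safety set does not settle the matter, since both documents let the SAP prevail. This shows the choice was stated openly. It does not explain why an endpoint described as efficacy should be grouped by drug received.

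As-received grouping is also not unique to NfL. A reader might infer that every other efficacy analysis here is by randomised arm, but the documents do not support that. W65PP and W78PP use actual treatment under the same 4.1.5 rule, and they are applied to the primary and secondary endpoints (SAP 7.3.3, 7.4.1, 7.4.2, 7.5). Those are supportive repeats, and receipt of incorrect treatment affecting the TFC is a ground for exclusion from them. For NfL, as-received is the only grouping stated.

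Two more inferences go too far. First, no sentence places the Objective (2) clinical-endpoint models in the Safety Population; that follows only from their position in 9.1.2, and 7.1.2 read literally gives mITT. Second, Objective (3) does not set out to estimate a treatment effect on TFC or cUHDRS. It tests the association with NfL change within treatment group, and it conditions on a post-randomisation variable, so regrouping would not turn it into a randomised comparison.

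The objection that the harm is hypothetical largely stands. Stopping drug or poor compliance relabels nobody; only sustained wrong supply does, in a blinded trial with IRT allocation. The mention of incorrect treatment in the per-protocol definitions is an example, not evidence that it occurred. Dilution does not favour either grouping in general: as-received does worse when f is below about one half and better above it. The case for grouping as randomised rests on keeping the allocated comparison.

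**Conclusion.** The point holds as a minor one. SAP 4.1.5 assigns an endpoint the SAP calls efficacy to a population grouped by drug received, under a cut-off suited to safety attribution. SAP 9.1.2 leaves the population for the Objective (2) treatment differences open to two readings, and 7.4.3 leaves the same gap for the log2(NfL) subgroups. The effect is zero if nobody received the wrong drug. Otherwise it is likely small: at most 2% dilution for five relabelled participants, and a shift of about 0.008 to 0.08 units for one to ten participants who differ by 1 unit. These sizes assume about 250 per arm and values of k, s and f that the documents do not give. The analyses are exploratory and outside the hierarchy, so no confirmatory conclusion depends on them.

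**What to change.** - In SAP 4.1.5, delete the reference to biomarker analysis, so that the safety set serves safety analyses only, as in Protocol 9.3.1.
- In SAP 9.1.2, state that treatment comparisons of log2(NfL) include treated participants with a Baseline and at least one post-baseline NfL value, grouped as randomised. Requiring mITT here would needlessly drop participants who have NfL data but no valid in-clinic TFC at Baseline or afterwards.
- In SAP 9.1.2, state that NfL-adjusted models of clinical endpoints use mITT, grouped as randomised, to match the main TFC and cUHDRS analyses.
- In SAP 7.4.3, name the population for the log2(NfL) subgroup analyses in the same way.
- Keep an as-received version as supportive if wanted.

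The cost is a few sentences, with the same data and models. SAP section 5 gives the route: an addendum before lock and unblinding, or the changes-to-analyses section of the CSR afterwards. Reporting the number of participants whose actual treatment differs from their randomised arm would show whether the choice made any difference.
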